## **Analyses**

Stata/SE 16.1 will be used for all statistical analysis.  
P value < .05 will be used for statistical significance.

Baseline characteristics will be compared between AST and no-AST groups using Chi-squared or Fisher's exact test for categorical data and t-test (normally distributed) or Wilcoxon rank-sum (not normally distributed) for continuous data. Primary outcome measures will be change in LASS and I-GERQ-R scores from initial visit to follow-up and change in airway and dysphagia symptoms assessed by chart review during the 1 year following the initial visit. The LASS and I-GERQ-R scores will be compared between initial and follow-up surveys using Wilcoxon signed-rank tests. Change scores (post-pre) will be calculated for LASS and I-GERQ-R, and differences in the improvement in scores based on laryngomalacia severity or randomization group will be evaluated using Wilcoxon rank-sum tests. Associations between LASS or I-GERQ-R and time between initial and follow-up surveys will be evaluated using Spearman rank correlation. Symptoms and weight at initial and follow-up visits will be compared using McNemar's and Wilcoxon signed-rank tests, respectively. Change in weight percentile based on laryngomalacia severity or randomization group will be evaluated using Wilcoxon rank-sum tests.

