# Study Outcomes

## Primary Outcome

- Airway Symptom Score Change From Consult (Baseline) to 3 Month Follow-up Appointment.
  - This will be parent-reported and measured using the Pittsburgh Airway Symptom Score (PASS) questionnaire. The PASS is a scale from 0-10 with a higher score indicating a worse outcome. This outcome will be assessed at the consult and the 3 month follow-up appointment.
- Infant Gastroesophageal Reflux Questionnaire (I-GERQ-R) Score Change From Consult (Baseline) to 3 Month Follow-up Appointment.
  - This will be parent-reported. There are 12 questions on the surveys on a scale of 0-42. A higher score indicates a worse outcome. Those with a score of  $\geq 16$  on this survey at the initial consult are excluded from the study, indicating true gastroesophageal reflux disease (GERD). This outcome will be assessed at the consult and the 3 month follow-up appointment.
- Change in Incidence of Airway Symptoms From Consult up to 1 Year Assessed Via Electronic Medical Chart Review.
  - Change in incidence of airway symptoms from consult up to 1 year assessed via electronic medical chart review. Notes from the Department of Otolaryngology will be reviewed which include reported symptoms from caregivers and symptoms seen upon exam. Airway symptoms included periods of apnea, chest wall retractions, cyanosis, stridor, noisy breathing, and increased respiratory rate.
- Change in Incidence of Dysphagia Symptoms From Consult up to 1 Year Assessed Via Electronic Medical Chart.
  - Change in incidence of dysphagia symptoms from consult up to 1 year assessed via electronic medical chart review. Notes from the Department of Otolaryngology will be reviewed which include reported symptoms from caregivers and symptoms seen upon exam. Dysphagia symptoms included choking, coughing, gagging with feeds and/or emesis after feeds.

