## Sample Size Calculation

Based on data from Dang et al [1], 62 participants per group will be needed to address the hypothesis that there is no difference in airway symptom improvement between AST and no-AST groups with alpha=.05 and power=.80 (two-tailed Fisher's exact test, G\*Power 3.1). Target enrollment will be 160 participants (80 in the AST group and 80 in the no-AST group, with 40 with mild laryngomalacia and 40 with moderate laryngomalacia in each group) to account for attrition.

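### Four unranked primary outcomes are each judged at an unadjusted .05, while the stated alpha and power cover only airway symptom improvement

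*Combined protocol and SAP*

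**What the plan says.** The Primary Outcome section of the combined protocol and SAP lists four items at the same level:

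- Airway score: "Airway Symptom Score Change From Consult (Baseline) to 3 Month Follow-up Appointment"
- Reflux score: "Infant Gastroesophageal Reflux Questionnaire (I-GERQ-R) Score Change From Consult (Baseline) to 3 Month Follow-up Appointment"
- Airway chart review: "Change in Incidence of Airway Symptoms From Consult up to 1 Year Assessed Via Electronic Medical Chart Review"
- Dysphagia chart review: "Change in Incidence of Dysphagia Symptoms From Consult up to 1 Year Assessed Via Electronic Medical Chart"

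The Analyses section repeats the same four as primary, calling the airway score LASS instead of PASS. I take the two names to mean the same scale. The significance rule is a single sentence: "P value < .05 will be used for statistical significance". No section ranks the outcomes, adjusts the threshold, or says how many primary results must be significant for the arms to be called different.

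The Sample Size Calculation covers one outcome: "62 participants per group will be needed to address the hypothesis that there is no difference in airway symptom improvement". It uses alpha .05, power .80 and a two-tailed Fisher's exact test.

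The Analyses section names a test by randomization group for only two of the four primaries, namely Wilcoxon rank-sum on the two questionnaire change scores. For symptoms it names only McNemar's test of initial against follow-up visits, which compares patients with themselves.

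**The concern.** The stated error rate and power describe one test on one outcome, but the plan allows a primary finding on any of four. Study Objectives predicts that outcomes will not differ between the arms. A significant difference on any one primary would therefore contradict the hypothesis, and nothing in the plan says how to weigh it against three that show nothing. If the arms are truly equal, the chance of at least one such result exceeds the nominal 5%.

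Scientific Background presents the trial as a step towards guidelines where no standard exists. A chance difference in either direction on one questionnaire could be read as a real effect, or lack of effect, of acid suppression.

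**Working it through.** **Inputs from the documents.** Four primary outcomes (Primary Outcome; Analyses). Threshold .05 per test (Analyses). Two named between-arm primary tests (Analyses). One further between-arm test, Fisher's exact on airway symptom improvement, implied by the Sample Size Calculation. 62 evaluable and 80 enrolled per group, so the implied attrition is 1 − 62/80 = 22.5%.

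**Assumptions.** Any one significant result counts as a difference; the arms are truly equal; correlations between test statistics are illustrative, since the documents give none.

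**The plan's own figure.** The 62 per group cannot be reproduced, because the two response rates behind it are not stated. Solving backwards with exact Fisher power, 62 per group gives 80% power at two-sided .05 for pairs such as 50% vs 24.5%, 70% vs 44%, 80% vs 55% or 90% vs 69%. The figure is plausible, and nothing here shows it to be wrong.

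**False-positive rate.** For k independent tests at .05 the chance of at least one false positive is 1 − 0.95^k.

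| Between-arm tests counted | k | Independent | Upper bound (k × .05) |
|---|---|---|---|
| Rank-sum on the two scores (named) | 2 | 1 − 0.95² = 9.75% | 10% |
| Plus Fisher on airway improvement (implied) | 3 | 1 − 0.95³ = 14.3% | 15% |
| Plus a dysphagia comparison (assumed) | 4 | 1 − 0.95⁴ = 18.5% | 20% |

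Simulation with equally correlated normal test statistics (1,000,000 draws) gave:

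| Pairwise correlation | 2 tests | 4 tests |
|---|---|---|
| 0.3 | 9.5% | 17.4% |
| 0.5 | 9.0% | 15.6% |
| 0.7 | 8.3% | 13.0% |
| 0.9 | 7.0% | 9.3% |

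Three tests were not simulated; at each correlation their rate lies between the two columns. Even the smallest count at the highest correlation stays above 5%.

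**Cost of keeping four primaries.** Holm's first step uses .05/4 = .0125. For the effect that 62 per group detects with 80% power at .05, exact Fisher power at .0125 is about 61% with 62 per group and about 75–77% if all 80 per group are evaluable.

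The normal approximation for the sample size ratio is [(z for .0125 two-sided + z for 80% power) / (z for .05 two-sided + z for 80% power)]² = 1.42, and 1.42 × 62 ≈ 88 evaluable per group. Exact Fisher calculations give 85–89. At 22.5% attrition that is 85/0.775 ≈ 110 to 89/0.775 ≈ 115 enrolled per group, against 80 planned.

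**The case against.** The strongest reply concerns size. A reader might infer that this trial's between-arm false-positive rate is 18.5%. That needs four between-arm tests, and the Analyses section names two. McNemar's test does not fill the gap: its null is no change over time, not equal arms. Scientific Background itself raises natural resolution, so a significant change over time may be real. This objection stands, and 18.5% is the figure for an assumed set of tests.

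A reader might also count the listed symptoms one by one (six airway, four dysphagia, plus two scores) and reach 1 − 0.95^12 = 46%. The documents do not support this. No section says each symptom will be compared between arms, and independence is implausible for overlapping items such as stridor and noisy breathing.

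Third, if all four outcomes had to be significant, there would be no inflation. That is correct, but no such rule is written, and a hypothesis of no differences across outcomes fits it poorly.

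Finally, the larger inferential risk may be reading non-significance as no difference. Adjustment does not address that, and a stricter threshold makes non-significance easier to reach. This is a fair limit on what the fix achieves. It does not remove the present defect.

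**Conclusion.** The point holds. Four unranked primaries, an unadjusted .05 for each and no decision rule leave the primary family without 5% control, and the stated alpha and power apply to only one of the four.

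On an any-one-significant reading with independent tests, the between-arm rate is about 10% for the tests the plan names and about 14% with the Fisher's exact test its sample size implies. It reaches 18.5% only if all four outcomes are compared between arms. Positive correlation reduces each figure without bringing it down to 5%. The absence of a hierarchy is certain from the text; the exact rate depends on how many between-arm tests are run and how correlated they are. The plan should be corrected, and it can be done in the SAP wording.

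**What to change.** 1. Name between-arm airway symptom improvement, the sized outcome, as the single primary outcome at two-sided .05.
2. Write into the Analyses section the between-arm Fisher's exact test that the Sample Size Calculation assumes, and define improvement for an individual patient. Without this, the sole primary outcome would have only a within-patient test.
3. Move PASS (LASS), I-GERQ-R and dysphagia symptoms to key secondary outcomes, either tested with Holm or reported as between-arm estimates with 95% confidence intervals.

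The cost is a change of SAP wording and the loss of primary status for three outcomes. The overall 5% is kept and no patients are added.

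If all four must stay primary, specify a between-arm test for each, apply Holm across the four, and restate the power using the .0125 figures above. These rest on back-solved response rates and should be recomputed from the rates actually used. That option has a material cost: keeping 80% power at the first step would mean about 220–230 enrolled in total against 160.

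Under either option, the SAP should say that a non-significant result is not in itself evidence of no difference.

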### Methods:

All Department of Pediatric Otolaryngology Airway clinic patients with a referral diagnosis of laryngomalacia will have their medical records screened for eligibility. All eligible families with infants that qualify for the study will be approached the day of clinic by their licensed physician to discuss the study. They will be given the Pittsburgh Airway Symptom Score (PASS) questionnaire and the Infant Gastroesophageal Reflux Questionnaire (I-GERQ-R) at the beginning of the appointment. The physician will then perform the standard procedures at the clinic appointment. The Flexible Laryngoscopy Findings sheet will be filled out in conjunction with the clinic procedures for objective data. The surveys will then be scored to determine true GERD (score  $\geq 16$ ) and severe laryngomalacia (LM) (RED questions on the PASS), which would further exclude these patients. There are 12 total questions on the I-GERQ-R. On the PASS, questions 1 & 2 are in the GREEN category and signifies mild LM, YELLOW signifies moderate LM, and RED is severe LM. On the PASS questionnaire, "Yes" to either #1 or #2 and

nothing else is mild LM, "yes" to at least one #3-5 and none of #6-10 is moderate LM, and "yes" to any of the #6-10" indicates severe LM. There are 10 total questions on the PASS.

Mild and moderate LM patients will be block randomized the day before the appointment to receive speech language therapy alone or speech language therapy with famotidine (Pepcid). Both treatments are standard of care in these patients as well as watchful observation. Speech language therapy is part of the normal clinic visit for LM patients. There is no gold standard of care for LM, therefore this trial is important to establish this. Patients will be randomized in both mild and moderate LM blocks before the appointment, as providers are unaware of the severity until the time of the appointment. After the appointment, if the family does not want to participate, the name will be taken off the randomization sheet completely or off the unused block.

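### The consult questionnaires both select infants and supply the baseline, so the before/after and by-severity tests of PASS and I-GERQ-R contain regression to the mean and should be descriptive only

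*Combined protocol and SAP*

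**What the plan says.** **Screening.** Under Methods, families complete both instruments once, on arrival: "They will be given the Pittsburgh Airway Symptom Score (PASS) questionnaire and the Infant Gastroesophageal Reflux Questionnaire (I-GERQ-R) at the beginning of the appointment". The sheets are then scored. An I-GERQ-R of 16 or more counts as true reflux disease, and any yes on PASS items 6-10 counts as "severe laryngomalacia (LM) (RED questions on the PASS), which would further exclude these patients". The Primary Outcome section repeats the reflux rule: infants at or above 16 "on this survey at the initial consult are excluded from the study". Methods also sets a lower limit. Mild disease needs a yes on item 1 or 2 and nothing else; moderate needs a yes on at least one of items 3-5 and none of 6-10.

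**Baseline.** The Primary Outcome section takes the same consult scores as the start of the change score: "This outcome will be assessed at the consult and the 3 month follow-up appointment". I-GERQ-R runs from 0 to 42 and PASS from 0 to 10; higher is worse on both.

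**Tests.** The Analyses section states: "The LASS and I-GERQ-R scores will be compared between initial and follow-up surveys using Wilcoxon signed-rank tests". It separately compares change scores by randomization group and by laryngomalacia severity with rank-sum tests. P below .05 is significant throughout. It does not say whether the signed-rank tests pool the arms. Analysis Inclusion limits the final analysis to infants who meet eligibility. No second baseline and no caution about regression to the mean is described.

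The Analyses section says LASS, undefined, where the rest of the document says PASS. I read them as one instrument, which is an assumption.

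**The concern.** A score used to admit infants is partly chance on the day. Keeping only those below a cut-off keeps some who scored low by luck, and they tend to score higher at the next visit. Requiring a symptom at entry does the reverse. The I-GERQ-R baseline cannot exceed 15 of 42 and the PASS baseline cannot exceed 5 of 10, while follow-up scores have no such limits.

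A before/after test cannot separate this artefact from natural resolution or a treatment effect. Two of the primary outcomes would carry P values that look like evidence about change in these infants. Real improvement in I-GERQ-R could be understated, or a stable group could seem to worsen. On PASS the error could go either way. Severity is read from the same PASS sheet, so a difference in change between mild and moderate infants can also arise from selection alone.

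**Working it through.** **The plan's own figure.** None is given for the before/after tests. The only stated sample size, 62 per group, concerns the comparison of arms. It is used here only to set the number of completers: 2 x 62 = 124.

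**Inputs from the documents.** Cut-off 16 and range 0-42 for I-GERQ-R; range 0-10, no yes on items 6-10 and at least one yes on items 1-5 for PASS; significance at .05.

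**Assumed inputs.** The screened I-GERQ-R mean, SD and test-retest correlation r, and the PASS item frequencies. The documents give none of these.

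**I-GERQ-R.** Take roughly normal scores with the same mean and SD at both visits, correlation r, and no true change. Among infants kept at 15 or below,

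expected rise = (1 - r) x SD x phi(a) / Phi(a), with a = (15.5 - mean) / SD.

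| Mean, SD, r | a | Rise in points | Significant worsening, n = 124 |
|---|---|---|---|
| 8, 6, 0.8 | 1.25 | 0.2 x 6 x 0.1826/0.8944 = 0.245 | about 10% |
| 10, 5, 0.85 | 1.10 | 0.15 x 5 x 0.2179/0.8643 = 0.19 | about 11% |
| 12, 6, 0.8 | 0.58 | 0.2 x 6 x 0.3365/0.7202 = 0.56 | about 44% |
| 13, 5, 0.7 | 0.50 | 0.3 x 5 x 0.3521/0.6915 = 0.76 | about 61% |
| 14, 6, 0.7 | 0.25 | 0.3 x 6 x 0.3867/0.5987 = 1.16 | about 84% |
| 16, 6, 0.6 | -0.08 | 0.4 x 6 x 0.3976/0.4668 = 2.04 | about 99% |

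The last column comes from simulating integer scores and applying the signed-rank test; the nominal rate in that direction is 2.5%. With 62 infants, as when each arm is tested alone, the mean-12 case falls to about 22% and the mean-14 case to about 51%. Putting the most favourable values together (mean 8, SD 5, r 0.85) gives a = 1.5 and a rise of only 0.15 x 5 x 0.1295/0.9332 = 0.10. The direction is the same in every case; the size is not fixed.

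**PASS.** Ten yes/no items were simulated with no true change, r from 0.5 to 0.85, 124 infants and both entry rules applied. Items 6-10 start at 0 and add 0.05 to 0.19. Items 1-5, where a yes was required, fall by 0.03 to 0.33. The net result depends on the assumed symptom frequency:

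- common symptoms: +0.07 to +0.15, significant in 12% to 26% of runs, almost all toward worsening;
- intermediate: about -0.05, significant in 6% to 9%;
- less common: -0.14 to -0.25, significant in 45% to 70%, all toward improvement.

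**Change by severity.** A mild infant starts at 0 on items 3-10; a moderate one has at least one yes on items 3-5. In the same PASS runs, the rank-sum test of change by severity rejected in 23% to 78%. This was run for PASS only. I-GERQ-R does not define severity, so its by-severity test is exposed only as far as the two scores share same-day error.

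**Between arms.** With the same selection and no true effect, the rank-sum test of change by arm rejected in 3% to 7% of runs for I-GERQ-R and 4% to 8% for PASS, about the nominal 5%.

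**The case against.** The strongest reply is that none of this touches the trial's question. The aim, the hypothesis and the sample size concern the two arms, and the test by randomization group keeps its error rate. That stands. A reader might infer that the primary treatment comparison is compromised; the documents do not support that, since the same cut-offs apply to both arms. Nor does the plan say that a signed-rank result will be read as a treatment effect.

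A reader might also infer that both before/after tests are biased toward worsening. For PASS they are not shown to be: the symptom required at entry pulls items 1-5 toward improvement, and the net sign depends on frequencies not given.

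Strictly, if scores drift through regression to the mean, the signed-rank null for the enrolled infants is false, and rejecting it is not a type I error. That is correct. The hazard lies in interpretation, and it remains because the plan gives these tests a significance threshold and no caution.

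The no-change scenario is also artificial, since Scientific Background names natural resolution. With an assumed 2-point true improvement in I-GERQ-R, simulated cases with mean 8-12 and r 0.8-0.85 still detected improvement in over 98% of runs. With mean 16 and r 0.6 the improvement was masked (-2 + 2.04 = +0.04), yet worsening appeared in only 3%. So false worsening is not the expected result; on I-GERQ-R the likelier harm is understated improvement.

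Finally, every size above rests on assumption, and the mean-16 case implies that 1 - 0.4668 = 53% of screened infants are excluded on I-GERQ-R, which nothing in the documents supports.

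**Conclusion.** The concern holds in a limited form. The double use of the consult scores is plain in the text, and the before/after tests of both instruments therefore include a selection artefact. For I-GERQ-R its direction is toward worsening whenever test-retest correlation is below 1. Its size is about 0.2 to 2 points in the tabulated cases, smaller at the most favourable corner, with about 10% to 99% significant worsening at n = 124 if nothing truly changes. For PASS the net direction is unknown. The PASS by-severity test is exposed through the same sheet. The between-arm comparison is not biased by this mechanism. The plan should be changed, because these are planned significance tests on listed primary outcomes, but the main randomized result does not depend on it.

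**What to change.** In the Analyses section:

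- Label the before/after signed-rank tests and the by-severity change tests for PASS/LASS and I-GERQ-R as descriptive, with no significance claim.
- Report initial and follow-up scores by arm.
- Base inference on the randomized between-arm comparison.
- State that within-group change reflects the entry cut-offs and natural resolution as well as any effect of care.
- Report by arm the proportion with I-GERQ-R of 16 or more and the proportion with any RED item at follow-up. Both start at 0% by design and need no new data.
- Use one name for the airway score, PASS or LASS.

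The cost is wording only: no added visits, data or infants. The downside is that the before/after and by-severity P values no longer serve as inference.

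### Arm tests on PASS and I-GERQ-R change use baseline only by subtraction and ignore the severity blocks: valid, but less precise than the collected data allow, and without an effect estimate

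*Combined protocol and SAP*

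**What the plan says.** The Analyses section is the only text on how the two questionnaire scores are tested. It states "Change scores (post-pre) will be calculated for LASS and I-GERQ-R", and then that "differences in the improvement in scores based on laryngomalacia severity or randomization group will be evaluated using Wilcoxon rank-sum tests". For inference it adds only that "P value < .05 will be used for statistical significance". It asks for no adjusted model, stratified arm test, effect estimate or interval for these scores.

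The Methods section builds severity into the allocation: "Patients will be randomized in both mild and moderate LM blocks before the appointment". The Sample Size Calculation plans 40 mild and 40 moderate infants in each arm.

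Methods also defines severity from the baseline PASS. Yes to item 1 or 2 and nothing else is mild; a yes "to at least one #3-5 and none of #6-10 is moderate LM"; any yes on items 6-10 is severe and excluded. On scoring, Methods says "There are 10 total questions on the PASS" and Primary Outcome says "The PASS is a scale from 0-10 with a higher score indicating a worse outcome". Infants scoring 16 or more on I-GERQ-R at the consult are excluded.

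**The concern.** Baseline score and severity are both known before treatment starts, and severity is a design variable. Subtracting baseline fixes its slope at one. When follow-up depends on baseline less steeply than that, the change score carries baseline noise that a covariate would remove. Ignoring the blocks also leaves in the test's error term a source of variation that the allocation has already balanced.

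The stake is the precision of the estimated effect of acid suppression on two of the four primary outcomes. The stated hypothesis is no difference, so readers will need an estimate and an interval, and the plan supplies only a significance threshold.

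A smaller matter concerns the PASS comparison by severity. If the same baseline items set both the severity group and the starting score, the two groups have different room to fall. A difference in raw change could then be misread as moderate infants responding better.

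**Working it through.** **Inputs from the documents.** 62 analysable infants per arm; equal mild/moderate split, so 31 per stratum per arm; two-sided 0.05; the PASS item rules; I-GERQ-R entry score below 16 on a 0-42 scale.

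**Assumed, because the documents are silent.** LASS is PASS; PASS counts yes answers (10 questions, 0-10 scale); all score distributions, correlations and resolution rates.

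**1. The plan's own figure.** The 62 per group is for a two-tailed Fisher test on airway improvement. The rates behind it are not given, so it cannot be reproduced. At 62 per arm, 80% Fisher power fits pairs such as 90% vs 68.6% or 60% vs 34.2%. The step to 160 implies 1 - 124/160 = 22.5% attrition. No power is stated for the score tests.

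**2. Validity.** Simulated null rejection for PASS was 3.6-5.2% for the rank-sum, 4.7-5.4% for van Elteren and 3.9-4.8% for the adjusted model. A second PASS-like model gave 3.0-4.4% for the rank-sum. For I-GERQ-R it was 4.0-6.6% (rank-sum) and 4.1-5.7% (adjusted). Under the null both arms' change scores come from one distribution, so the nominal level applies and I read the spread around 5% as simulation error.

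**3. PASS variance by hand.** Let b be the baseline count and p the chance that an item resolves, with no new symptoms. Within a stratum, Var(change) = residual + p²Var(b); adjustment removes the second term. The residual is p(1-p)E(b) if items resolve independently and p(1-p)E(b²) if all or none. Take p = 0.50 and 0.65 in the two arms: mean p(1-p) = (0.25 + 0.2275)/2 = 0.23875; mean p² = (0.25 + 0.4225)/2 = 0.33625.

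Mild b is 1 or 2 with equal chance: mean 1.50, variance 0.25, E(b²) 2.5. Moderate b is 1-5 with chances .10/.25/.35/.20/.10: mean 2.95, E(b²) 9.95, variance 9.95 - 2.95² = 1.2475. Averages over strata: E(b) 2.225, E(b²) 6.225, Var(b) 0.749. The baseline term is 0.33625 × 0.749 = 0.252.

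- Independent: 0.23875 × 2.225 = 0.531; ratio 0.531/(0.531 + 0.252) = 0.68.
- All or none: 0.23875 × 6.225 = 1.486; ratio 1.486/(1.486 + 0.252) = 0.86.

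With a flat moderate baseline (.20 each; averages 2.25, 6.75 and 1.125) the ratios are 0.537/0.915 = 0.59 and 1.612/1.990 = 0.81. A common slope across arms raises these by under 0.01.

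**4. PASS power by simulation.** 36 scenarios: three moderate baselines (the two above and a low one, .30/.30/.20/.12/.08), new-symptom chance 0, 5 or 10% per absent item, four resolution patterns; 2,000-3,000 replicates each; resolution 50% vs 65%.

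| Resolution across infants | Rank-sum | Adjusted, HC3 | Gain, points | Variance ratio |
|---|---|---|---|---|
| Independent, same p for all | .22-.47 | .29-.71 | 7 to 31 | .57-.78 |
| Moderate variation (beta, concentration 4) | .22-.43 | .28-.56 | 6 to 16 | .66-.78 |
| Strong variation (beta, concentration 1) | .21-.37 | .23-.43 | 2 to 7 | .73-.83 |
| All or none | .19-.33 | .21-.32 | -3 to +1 | .80-.87 |

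Repeat runs put the variance reduction at about 12-42%, so the upper ratio is about 0.88. With 8,000 replicates the largest power gain found was 28 points.

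These gains mix covariate, stratification and type of test. Against van Elteren, the adjusted model gained 4-18, 3-10, 1-4 and -4 to +1 points in the four rows (new-symptom chance 0 and 10%).

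**5. I-GERQ-R.** Baseline was limited to 0-15, follow-up was clipped to 0-42 with an assumed 3-point mean fall, and the effect was set for about 80% adjusted power. Rank-sum against adjusted power was .57-.68 against .76-.77 at baseline-follow-up correlation 0.2, and .68-.74 against .76-.78 at 0.8. The variance ratio was .68-.94.

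A formula isolates the covariate: ratio = (1-r²)/[(1-r²) + (1-r)²v], where v is the share of baseline variance left after the entry limit (0.28-0.55 here). At r = 0.2, v = 0.55: 0.96/(0.96 + 0.64 × 0.55) = 0.73, and raw-change power is 67% against 80%. At r = 0.8, v = 0.28: 0.36/(0.36 + 0.04 × 0.28) = 0.97, and 79% against 80%.

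**6. PASS change by severity.** Mild infants start at 1-2 and moderate infants at 1-5. With the same p and new-symptom chance q in both groups, E(change) = 10q - (p+q)b, so the groups differ by (p+q) times the baseline gap: 1.45, 1.50 or 0.88 for the three baselines. With q = 0 the moderate fall is 2.95/1.50 = 1.97, 3.00/1.50 = 2.00 or 2.38/1.50 = 1.59 times the mild fall. A raw-score arm-by-severity interaction inherits this: the same per-item benefit of 0.15 in both groups gives 0.15 × 1.45, 1.50 or 0.88 = 0.22, 0.23 or 0.13 points.

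**The case against.** The strongest reply is that the planned test is sound and the rest is preference. A rank test on a short bounded score is a defensible choice, it keeps its level, and no stated power is breached. The documents give no distribution, correlation or effect size, so every gain above is assumed. The largest gain needs symptoms of one condition in one infant to resolve independently with a common probability, the least plausible of the four patterns. Simply stratifying the planned test would be a smaller change.

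Much of this stands. The power figures are illustrative and mix three causes, so the variance ratios are the better summary, and the top gain should not be the headline. The preference argument does not stand: the adjusted variance was lower in all 36 PASS scenarios, including those with no power gain, and the data are already collected. Van Elteren alone recovers part of the power, but gives no effect estimate or interval.

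A reader might infer more than the documents support:

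- *That the arm test is biased or the trial underpowered on these scores.* The test holds its level, and no power was claimed for the scores.
- *That adjustment would let a non-significant result show no difference.* It would not; that is a separate issue.
- *That the severity comparison has a high false-positive rate or contaminates the arm result.* In one set of simulations it was significant in 93-100% of trials with equal per-item resolution. But mean raw change really does differ there; this is mathematical coupling. The contrast lies outside the stated aim and outcomes, and the arm conclusion does not depend on it.

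**Conclusion.** The point holds as a loss of precision and a missing estimate on two of four primary outcomes. It is not a matter of bias or of invalidity.

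Under the stated assumptions the adjusted difference has about 0.57-0.88 of the variance of the raw mean-change difference for PASS, and about 0.68-0.94 for I-GERQ-R. The PASS power gain over the planned test is typically a few to about 16 points when resolution varies between infants, up to about 30 only under independent resolution with one common probability, and nil under all-or-none resolution. Confidence is firm on direction and medium on size.

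The PASS change by severity needs a reporting note only. It rests on PASS counting yes answers and does not extend to I-GERQ-R, whose items do not define severity.

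**What to change.** Amend the SAP before the data are analysed:

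- For each score, prespecify one primary arm analysis: a linear model of follow-up score on arm, baseline score and severity stratum, with HC3 standard errors, reporting the adjusted difference and its 95% confidence interval. Severity belongs in the model because it defines the randomisation blocks.
- Keep a van Elteren test on change, stratified by severity, as the rank-based check.
- Report PASS change by severity descriptively (baseline, follow-up, share of baseline items resolved), without reading it as differential improvement.
- Do not use a raw-score arm-by-severity interaction for PASS. If effect differences by severity are explored, use a per-item scale such as the share of baseline items resolved.
- State how PASS is scored and whether LASS is PASS.

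This needs no new data or visits. The cost is a change of estimand: from a rank comparison of change to an adjusted mean difference on a short bounded score, averaged over strata in which the raw-score effect may differ. If symptoms resolve all or none, the PASS power gain is nil, though the interval is still gained.
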